6.4 Study Intervention Compliance

The following measures will ensure that the study interventions are administered as planned and that any noncompliance is documented so that it can be accounted for in the data analyses:

- All vaccinations will be administered by qualified and trained study personnel
- The person in charge of study intervention management at the site will maintain accountability records of study intervention delivery to the study site, study intervention inventory at the site, dose(s) given to each participant, and unused or wasted doses

6.5 Concomitant Therapy

At the time of enrollment, ongoing medications and other therapies (eg, blood products) should be recorded in the source document as well as new medications prescribed for new medical conditions / AEs during study participation.

Documentation in the CRF of ongoing concomitant medication(s) will be limited to specific categories of medication(s) of interest beginning on the day of first vaccination. This may include medications of interest that were started prior to the day of vaccination or stopped prior to enrollment.

Reportable medications will be collected in the CRF from the day of each vaccination to the end of the solicited and unsolicited follow-up period after each vaccination, with the exception of influenza vaccination which will be collected throughout the study.

Reportable medications include medications that impact or may impact the consistency of the safety information collected after any vaccination and/or the immune response to vaccination. Three standard categories of reportable medications are defined:

- Category 1: medications impacting or that may have an impact on the evaluation of the safety (eg, antipyretics, analgesics, and non-steroidal anti-inflammatory drugs [NSAIDs], systemic steroids/corticosteroids)
- Category 2: medications impacting or that may have an impact on the immune response (eg, hydroxychloroquine, other vaccines, blood products, antibiotic classes that may interfere with bioassays used by the Global Clinical Immunology [GCI] department or other testing laboratories, systemic steroids/corticosteroids, immune-suppressors, immune-modulators with immunosuppressive properties, anti-proliferative drugs such as DNA synthesis inhibitors)
- Category 3: medications impacting or that may have an impact on both the safety and the immune response (eg, systemic steroids/corticosteroids)

Dosage and administration route, homeopathic medication, topical and inhaled steroids, as well as topical treatments, ophthalmic and ear treatments will not be recorded. Topical analgesics should not be applied at the site of vaccination; however, if they are applied inadvertently to the vaccination site, they should be recorded as a Category 1 medication in this specific instance.

Medications given in response to an AE will be captured in the “Action Taken” section of the AE CRF only. No details will be recorded in the concomitant medication CRF unless the medication(s) received belongs to one of the pre-listed categories. Medications will not be coded.

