1.3 Schedule of Activities (SoA)

Visits and procedures are detailed in the Operating Guidelines.

Table 1.1: Schedule of activities 1 (Cohort 1)

Phase I/II Study, 7 Visits, 1 Telephone Call, 1 Injection, 6 Blood Sample Time-points, Approximately 12 Months' Duration Per Participant

Visit (V) / Contact	Collection of information in the CRF	V01	V02	V03	V04	Telephone Call	V05	V06	V07 or Safety Follow-up Call§§§
Study timelines (Day [D])		D01	D09	D22	D36	D43	D113	D181	D366
Time Interval (days)			V01 + 8 days	V01 + 21 days	V01 + 35 days	V01 + 42 days	V01 +112 days	V01 + 180 days	V01 + 365 days
Time windows (days)		N/A	[+2 days]	[+7 days]	[+7 days]	[+2 days]	[+7 days]	[+14 days]	[+14 days]
Visit procedures:									
Informed consent	X	X							
Point-of-care SARS-CoV-2 antibody test		X							
Inclusion/exclusion criteria	X	X							
Collection of demographic data	X	X							
Collection of medical history	X Significant Medical History	X							
Physical examination*		X							
Pre-vaccination temperature		X							
Urine pregnancy test (if applicable) †		X							
Contact IRT system for randomization, participant number, and unique dose number allocation.	X	X							
Respiratory sample collection									Can occur at any time during the study as unscheduled visit(s)

Visit (V) / Contact	Collection of information in the CRF	V01	V02	V03	V04	Telephone Call	V05	V06	V07 or Safety Follow-up Call\$\$\$\$
Study timelines (Day [D])		D01	D09	D22	D36	D43	D113	D181	D366
Time Interval (days)			V01 + 8 days	V01 + 21 days	V01 + 35 days	V01 + 42 days	V01 +112 days	V01 + 180 days	V01 + 365 days
Time windows (days)		N/A	[+2 days]	[+7 days]	[+7 days]	[+2 days]	[+7 days]	[+14 days]	[+14 days]
Visit procedures:									
Clinical safety laboratory assessments ‡ (10 mL) (All participants)	X	X§	X						
Serum samples for Ab assays (30 mL) (All participants)	X	BL0001§		BL0002	BL0003		BL0004	BL0005	BL0006
Vaccination (VAC)	X	X							
Immediate surveillance (30 minutes)	X	X							
Diary Card provided		DC1**		DC2§§	DC3***		DC4†††	DC5†††	
Diary Card reviewed			DC1††			DC3††			
Diary Card collected				DC1‡‡	DC2‡‡		DC3‡‡	DC4‡‡	DC5‡‡
Collection of solicited injection site & systemic reactions	X	D01-D08							
Collection of unsolicited AEs	X	D01-D22							
Collection of concomitant medications	X Reportable concomitant medication	All reportable concomitant medications (including influenza vaccination)			Influenza and COVID-19 vaccinations only				

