** Participants will use this DC1 to record information about solicited reactions, unsolicited AEs, SAEs, and AESIs from D01 to D08 after vaccination and will continue to record information about unsolicited AEs, SAEs, and AESIs from D09 to V02.

†† The Investigator or an authorized designee will remind the participants to bring back the DC at the next visit and will answer any questions.

‡‡ The Investigator or an authorized designee will interview the participants to collect the information recorded in the DC and will attempt to clarify anything that is incomplete or unclear.

§§ Participants will use this DC2 to record solicited reactions, unsolicited AEs, SAEs, and AESIs (from V02 to V03) and will continue to collect unsolicited AEs, SAEs, and AESIs (from V03 to V04).

*** Participants will use this DC3 for unsolicited AEs follow-up until D43 and SAEs, AESIs, and COVID-19-like illness follow-up from V04 to V05.

††† Participants will use this DC4 for SAEs, AESIs, and COVID-19-like illness follow-up from V05 to V06.

‡‡‡ Participants will use this DC5 for SAEs, AESIs, and COVID-19-like illness follow-up from V06 to V07.

§§§ During the D09 telephone call, staff will review the DC1 for solicited reactions from D01 to D08 after vaccination, inquire whether the participant experiences any SAE or AESI not yet reported, and remind the participant to bring back DC1 for V02. This telephone call will NOT be documented in the CRF.

**** Prior to these specified time-points, active surveillance will still occur during the established contacts (phone calls and visits).

†††† AESIs (serious and non-serious) will be collected throughout the study as SAEs to ensure that events are communicated to the Sponsor in an expedited manner and followed-up until the end of the follow-up period or resolution, as per the assigned causal relationship. These include: Anaphylactic reactions, Generalized convulsion, Thrombocytopenia, Lacrimal and salivary disorders (tearing, dry mouth, dry eyes), any new-onset chronic medical conditions, and potential immune-mediated diseases.

†††† In case of participant discontinuation at a visit, the entire visit will be completed.

§§§§ During the D43 telephone call, staff will review the DC3 pertaining to unsolicited AEs, SAE, AESI, and COVID-19-like illness between V04 and the call and will remind the participant to bring back the DC3 for V05. This telephone call will NOT be documented in the CRF.

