5.2 Exclusion Criteria

Participants are not eligible for the study if any of the following criteria are met:

E01: Participant is pregnant, or lactating, or of childbearing potential and not using an effective method of contraception or abstinence from at least 4 weeks prior to the first vaccination until at least 12 weeks after the last vaccination. To be considered of non-childbearing potential, a female must be post-menopausal for at least 1 year or surgically sterile.

E02: Participation at the time of study enrollment (or in the 30 days preceding the first study vaccination) or planned participation during the present study period in another clinical trial investigating a vaccine, drug, medical device, or medical procedure

E03: Receipt of any vaccine in the 30 days preceding the first study vaccination or planned receipt of any vaccine in the 30 days following the last study vaccination except for influenza vaccination, which may be received at least 2 weeks before and a minimum of 2 weeks after study vaccines.^a

E04: Prior administration of a coronavirus vaccine (severe acute respiratory syndrome coronavirus 2 [SARS-CoV-2], SARS-CoV, Middle East Respiratory Syndrome [MERS-CoV])

E05: Receipt of immune globulins, blood or blood-derived products in the past 3 months

E06: Known or suspected congenital or acquired immunodeficiency; or receipt of immunosuppressive therapy, such as anti-cancer chemotherapy or radiation therapy, within the preceding 6 months; or long-term systemic corticosteroid therapy (prednisone or equivalent for more than 2 consecutive weeks within the past 3 months)

E07: History of SARS-CoV-2 infection, confirmed either clinically, serologically^b, or microbiologically

E08: Known systemic hypersensitivity to any of the vaccine components, or history of a life-threatening reaction to a vaccine containing any of the same substances^c

E09: Self-reported thrombocytopenia, contraindicating intramuscular (IM) vaccination based on Investigator's judgment

E10: Bleeding disorder, or receipt of anticoagulants in the 3 weeks preceding inclusion, contraindicating IM vaccination based on Investigator's judgment

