^a While receipt of any vaccine as listed in this criterion is exclusionary for this study, enrolled participants are free to receive an authorized/approved COVID-19 vaccine during the follow-up period. As efficacy has not been demonstrated for any of the investigational formulations under evaluation in the current study, it is not required to unblind participants to the VAT00001 study assignment prior to administration of an authorized COVID-19 vaccine. If the participant receives the authorized/approved vaccine, this information would be collected and the participant's data up to the point of receipt of authorized/approved vaccine will be included in the primary analysis for immunogenicity and safety. Participants will continue to be followed for the duration of the trial as per scheduled visits and procedures. (see [Section 7.1.2: Definitive Contraindications](#)).

^b Potential study participants will need to have a negative SARS-CoV-2 antibody test at time of enrollment.

^c The components of SARS-CoV-2 Recombinant Protein vaccine are listed in [Section 6.1](#) and in the SARS-CoV-2 Recombinant Protein Investigator's Brochure. In addition, information for the AF03 adjuvant are listed in the AF03 Investigator's Brochure.

E11: Deprived of freedom by an administrative or court order, or in an emergency setting, or hospitalized involuntarily

E12: Current alcohol abuse or drug addiction

E13: Chronic illness or condition considered to potentially increase the risk for severe COVID illness^a (26) or that, in the opinion of the Investigator, is at a stage where it might interfere with study conduct or completion^b

E14: Moderate or severe acute illness/infection (according to Investigator judgment) on the day of vaccination or febrile illness (temperature $\geq 38.0^{\circ}\text{C}$ [$\geq 100.4^{\circ}\text{F}$]). A prospective participant should not be included in the study until the condition has resolved or the febrile event has subsided

E15: Receipt of any therapy known to have in-vitro antiviral activity against SARS-CoV-2^c within 72 hours prior to the first blood draw

E16: Identified as an Investigator or employee of the Investigator or study center with direct involvement in the proposed study, or identified as an immediate family member (ie, parent, spouse, natural or adopted child) of the Investigator or employee with direct involvement in the proposed study

E17: Residence in a nursing home or long-term care facility

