7.1 Discontinuation of Study Intervention

[Section 7.1.1](#) and [Section 7.1.2](#) are applicable to Cohort 2 only.

These sections are not applicable to Cohort 1 as they are planned to receive only 1 vaccination in the study.

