8.4.1 Time Period and Frequency for Collecting AE and SAE Information

Immediate Post-vaccination Observation Period

Participants will be kept under observation for 30 minutes after each vaccination to ensure their safety. The post-vaccination observation should be documented in the source document.

Reactogenicity

Solicited injection site reactions will be collected from D01 to D08 after each vaccination.

Solicited systemic reactions will be collected from D01 to D08 after each vaccination.

The solicited injection site reactions and systemic reactions that are pre-listed in the diary cards and CRF, together with the intensity scales, are presented in [Appendix 10.3.5.1.1](#).

Unsolicited Adverse Events

Unsolicited AEs include unsolicited non-serious AEs and SAEs. The intensity grading scale for unsolicited non-serious AEs is presented in [Appendix 10.3.5.1.2](#).

Unsolicited non-serious AEs will be collected from D01 to D22 after each vaccination.

SAEs will be collected and assessed throughout the study, from inclusion until 12 months after the last vaccination (up to D366 for Cohort 1 and up to D387 for Cohort 2). However, before the first study intervention administration, only SAEs related to study procedures are to be collected (eg, SAEs related to blood sampling).

Medical occurrences that begin before the start of study intervention but after obtaining informed consent will not be recorded on the AE section of the CRF.

All SAEs will be recorded and reported to the Sponsor or designee immediately and under no circumstance should this exceed 24 hours, as indicated in [Appendix 10.3](#). The Investigator will submit any updated SAE data to the Sponsor within 24 hours of it being available.

Investigators are not obligated to actively seek AE or SAE after conclusion of the study participation. However, if the Investigator learns of any SAE, including a death, at any time after a participant has been discharged from the study, and he/she considers the event to be reasonably related to the study intervention or study participation, the Investigator must promptly notify the Sponsor.

Medically Attended Adverse Events (MAAEs)

MAAEs will be collected at any time during the study.

Adverse Events of Special Interest (AESIs)

AESIs will be collected at any time during the study.

See [Section 8.4.6](#) for the list of AESIs.

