5.2.3 Per-Protocol Analysis Set

Subset of the FAS. Participants presenting with at least one of the following conditions will be excluded from the PPAS:

- Participant did not meet all protocol-specified inclusion criteria or met at least one of the protocol-specified exclusion criteria
- Participant did not complete the protocol-defined vaccination schedule
- Participant received a study intervention other than the one that he / she was randomized to receive
- Preparation and / or administration of study intervention was not done as per-protocol
- Participant did not receive study intervention in the proper time window as defined in the protocol visits.
- Participant received a Category 2 or Category 3 therapy /medication / as stated in Section 6.5 of the Protocol
- Participant with positive test results in the neutralization test at baseline.

The above conditions leading to exclusion from the PPAS may be detailed and completed if necessary following the data review. In any case, if PPAS definition is modified, the PPAS definition will be finalized before the database lock and documented in an SAP update.

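### Category 2/3 medication is systematically collected to D22 in Cohort 1 but to D43 in Cohort 2, so an undated per-protocol exclusion screens the two cohorts unequally before the primary D36 titre.

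*Protocol*

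**What the plan says.** - **Collection rule.** Protocol 6.5 records reportable medication in the CRF from each vaccination "to the end of the solicited and unsolicited follow-up period after each vaccination". Protocol 8.4.1 sets the length of that period: "Unsolicited non-serious AEs will be collected from D01 to D22 after each vaccination".
- **Cohort 1.** There is one injection, at D01. Protocol 7.1 says of its contraindication subsections: "These sections are not applicable to Cohort 1 as they are planned to receive only 1 vaccination in the study". In Table 1.1 the later part of the concomitant-medication row reads "Influenza and COVID-19 vaccinations only".
- **Cohort 2.** The second injection is at D22. A footnote to Table 1.2 gives the end of unsolicited follow-up: "Participants will use this DC3 for unsolicited AEs follow-up until D43".
- **Exclusion rule.** SAP 5.2.3 removes a participant from the PPAS on this condition: "Participant received a Category 2 or Category 3 therapy". Protocol 9.3 has the same condition. Both point to Protocol 6.5 for the categories, and neither gives a date limit or links the exposure to a particular sample.
- **Use.** Neutralizing titres at D01, D22 and D36 are primary in every group (Protocol Table 3.1). The main immunogenicity analysis is on the PPAS-IAS, a subset of the PPAS. SAP 5.1.1.4 summarizes the primary endpoints by arm and by injection schedule (1-injection N=120, 2-injection N=240). Protocol 9.4.2.1 allows a D36 regression with schedule as an explanatory variable.

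**The concern.** Choosing between one and two injections is a stated purpose of the study, and Protocol 4.2 names the D22 and D36 titres as the basis for that choice. The per-protocol filter is meant to remove titres that may be altered by drugs such as systemic steroids, immunosuppressants or blood products. Here it depends on a collection window that was set for adverse events and closes 21 days earlier in one cohort.

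Take a systemic steroid course starting on D25. In Cohort 2 it falls inside the collection window and excludes the participant. In Cohort 1 no routine medication entry is required, so the D36 titre would normally be analysed as per protocol. The D36 one- versus two-injection summary then compares a fully screened group with a partly screened one.

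The rule also errs the other way. The PPAS is a single set for all time points, so use after the D36 draw but before D43 removes a Cohort 2 participant's earlier titres, which that drug could not have affected.

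**Working it through.** **Collection windows** (end = injection day + 21)
- Cohort 1: D01 + 21 = D22.
- Cohort 2: D22 + 21 = D43. This reproduces the day in the Table 1.2 footnote.
- If the second injection is given at the end of its +7-day window (D29), collection runs to D29 + 21 = D50.

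**Interval before the D36 sample**
- Cohort 1, nominal V04: D23 to D36 = 36 - 22 = 14 days, out of 35 days after D01 (14/35 = 40%).
- Cohort 1, V04 at the end of its +7-day window (D43): 43 - 22 = 21 days, out of 42 (50%).
- Cohort 2: V04 is at second injection + 14 [+7] days, so at most + 21. Collection also runs to + 21. Days not covered: 0.

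**Interval after the nominal Cohort 2 D36 sample that still triggers exclusion**
- D37 to D43 = 43 - 36 = 7 days.

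**Cohort sizes** (Protocol Table 4.2)
- Cohort 1: 5 x 20 + 5 x 10 = 150, of whom 120 receive vaccine.
- Cohort 2: (20+60+20+60+20+20) + (10+30+10+30+10) = 200 + 90 = 290.

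**Expected numbers.** The documents give no rate of Category 2/3 use, so 2-5% per 30 days is an assumption, constant over time.
- Cohort 1, D23-D36 not screened: 150 x 14/30 x (0.02 to 0.05) = 1.4 to 3.5. Vaccinees only: 120 x 14/30 x (0.02 to 0.05) = 1.1 to 2.8.
- Cohort 1, if every V04 were at D43: 150 x 21/30 x (0.02 to 0.05) = 2.1 to 5.3.
- Cohort 2, exposed on D37-D43: 290 x 7/30 x (0.02 to 0.05) = 1.4 to 3.4. This slightly overstates those exposed only then.

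**Wider range.** Let r be the assumed chance of at least one such medication per 21 days, with a constant hazard h = -ln(1 - r)/21 and probability 1 - exp(-h x days):

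| r per 21 days | Cohort 1 share excluded (21 days) | Cohort 2 share excluded (42 days) | Cohort 1 exposed in D23-D36, of 150 | Cohort 2 exposed only in D37-D43, of 290 |
|---|---|---|---|---|
| 1% | 1.0% | 2.0% | 1.0 | 1.0 |
| 3% | 3.0% | 5.9% | 3.0 | 2.8 |
| 5% | 5.0% | 9.8% | 5.0 | 4.5 |
| 10% | 10.0% | 19.0% | 10.2 | 8.4 |

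At the same underlying rate of use, Cohort 2 loses about twice the share of participants that Cohort 1 does. Cohort 1 arm-by-age cells hold 10 or 20, so one participant is 5-10% of a cell.

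**The case against.** The strongest defence is that a window per injection is coherent. Both cohorts are covered for 21 days after each injection, and a drug taken on D25 is 24 days after the only injection in Cohort 1 but 3 days after the second in Cohort 2. That explains the adverse-event window. It does not justify an undated exclusion applied to a D36 sample that is primary in both cohorts.

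These points stand and limit the finding:
- **A reader might infer that Cohort 1 use after D22 is invisible.** The documents do not support that. Medically attended, serious and special-interest events are collected throughout, and their treatment goes to the Action Taken field. Treatment of COVID-19-like illness is recorded. Protocol 6.5 puts newly prescribed medication in source documents. Influenza and COVID-19 vaccines are collected throughout in both cohorts. What is missing is systematic CRF collection, and a stated route from these other records to the PPAS.
- **A reader might infer that every schedule comparison is affected.** The SAP 5.1.1.4 regression takes Cohort 1 at D22 and Cohort 2 at D36, and collection before Cohort 1's D22 sample is complete.
- **SAP 5.2.5 confirms the immunogenicity results on the FAS**, where this filter does not operate, and all analyses are descriptive. This shows whether the filter matters, but it does not make the PPAS-IAS comparison like for like.
- **A reader might add that vaccines barred for 30 days go uncollected in the last 9.** Exclusion criterion E03 concerns "planned receipt of any vaccine in the 30 days following the last study vaccination". It is judged on intention at enrolment, so later unplanned receipt is not a breach of it.
- **A reader might add assay interference by antivirals at later draws.** Criterion E15 ("Receipt of any therapy known to have in-vitro antiviral activity against SARS-CoV-2") applies only before the first draw, and the assay measures infectivity. The documents do not give interference as the reason for E15 and have no data on later draws, so this is at most a secondary remark.

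**Conclusion.** The inconsistency is real and follows from the documents' own day counts. One exclusion criterion is screened over the whole interval before D36 in Cohort 2 and up to D22 only in Cohort 1, and no section reconciles the two. It touches the D36 by-arm and one- versus two-injection summaries and the Protocol 9.4.2.1 D36 model.

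The expected size is small: about 1 to 4 of 150 Cohort 1 participants not screened out, and about 1 to 3 of 290 Cohort 2 participants excluded for use after the nominal sample. Both rest on the assumed 2-5% use per 30 days. The rate may be lower, since the entry criteria on immunosuppression, chronic illness and autoimmune disease remove many likely users. The direction of any effect on the titres cannot be stated, because Category 2/3 covers drugs with different effects on immune response or assay. The documents do not support a conclusion that the schedule choice would be wrong. The finding is that the per-protocol comparison at D36 is not like for like, and that this can be put right cheaply.

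**What to change.** 1. **Protocol 6.5 and Table 1.1:** collect Category 2 and 3 medication in the CRF up to the V04 (D36) sample in Cohort 1, as already happens in Cohort 2.
2. **Where V04 has passed:** retrieve use between D23 and V04 from the source documents that Protocol 6.5 already requires, before final lock. This is the likely route, since Protocol 9.5 reports a partial database lock by Amendment 1.
3. **SAP 5.2.3:** apply the Category 2/3 exclusion per sample, dropping only samples drawn after the exposure. The SAP already works this way elsewhere: 5.2.3.1 drops individual out-of-window samples and keeps the participant, and 5.1 keeps data from before a non-study COVID-19 vaccine. SAP 5.2.3 permits such a change before database lock through an SAP update.

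Cutting the exclusion back to D01-D22 in both cohorts is not a good substitute. It would remove the filter from the 14 days after Cohort 2's second injection, which matter most for its D36 titre.

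**Cost:** a few extra CRF entries or source checks, one SAP sentence, and possibly a few more Cohort 1 D36 samples leaving the PPAS-IAS. Final D36 tables may differ slightly from the interim ones, and the report should say why. Systematic medication screening before the six- and twelve-month samples remains limited in both cohorts. Those are secondary endpoints, and a sentence acknowledging this is enough.

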7.1.1 Temporary Contraindications

Should a participant experience one of the conditions listed below, the Investigator will postpone further vaccination until the condition is resolved. Postponement must still be within the timeframe for vaccination indicated in the SoA.

TCI01: Febrile illness (temperature $\geq 38.0^{\circ}\text{C}$ [$\geq 100.4^{\circ}\text{F}$]) or moderate or severe acute illness / infection on the day of vaccination, according to Investigator judgment

TCI02: Receipt of any vaccine (other than the study vaccine[s]) in the 21 days preceding the second study vaccination or planned receipt of any vaccine in the 30 days following the second study vaccination except for influenza vaccination, which may be received at least 2 weeks before and a minimum of 2 weeks after study vaccines. This exception includes monovalent pandemic influenza vaccines and multivalent influenza vaccines.

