9.3 Populations for Analyses

The following populations are defined:

Population	Description
Randomized	All participants with a randomized group that has been allocated by IRT
Safety Analysis Set (SafAS)	Subset of randomized participants who have received at least one injection of study intervention. Participants will have their safety analyzed according to the study intervention they actually received. Safety data recorded for a vaccine received out of the protocol design will be excluded from the analysis (and listed separately).
Full analysis set (FAS)	Subset of randomized participants who received at least 1 injection of the study intervention. Participants will be analyzed according to the study intervention group to which they were randomized.
Per-protocol analysis set (PPAS)	Subset of the FAS. Participants presenting with at least one of the following relevant conditions will be excluded from the PPAS: 
 • Participant did not meet all protocol-specified inclusion criteria or met at least one of the protocol-specified exclusion criteria • Participant did not complete the protocol-defined vaccination schedule • Participant received a study intervention other than the one that he / she was randomized to receive • Preparation and / or administration of study intervention was not done as per-protocol • Participant did not receive study intervention in the proper time window • Participant received a Category 2 or Category 3 therapy / medication / as stated in Section 6.5 • Participant with positive test results in the ELISA and/or neutralization test at baseline • Additional conditions for exclusion may be identified during the review of protocol deviations; such conditions will be documented in the Statistical Analysis Plan (SAP)
Per-protocol analysis set for immunogenicity (PPAS-IAS)	Subset of PPAS excluding participants who provided all post-dose serology samples outside the proper time window or no post-dose serology sample was drawn.
Per-protocol analysis set for CMI (PPAS-CMI)	Subset of PPAS excluding participants who provided all post-dose CMI samples outside the proper time window or no post-dose CMI sample was drawn.

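### Influenza vaccine that the protocol permits counts as a Category 2 medication, so participants who follow the protocol can leave the per-protocol sets and lose valid D22 and D36 data

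*Protocol*

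**What the plan says.** **Permission.** E03 in Protocol 5.2 bars other vaccines around the study injections "except for influenza vaccination, which may be received at least 2 weeks before and a minimum of 2 weeks after study vaccines". TCI02 in Protocol 7.1.1, which governs the second injection in Cohort 2, repeats this and adds: "This exception includes monovalent pandemic influenza vaccines and multivalent influenza vaccines".

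**Classification.** Protocol 6.5 defines Category 2 as products that affect, or may affect, the immune response. Its examples include "hydroxychloroquine, other vaccines, blood products", and influenza vaccine is not carved out. Reportable medications are recorded to the end of the follow-up period after each injection, "with the exception of influenza vaccination which will be collected throughout the study". Both schedule-of-activities tables name influenza vaccination as reportable.

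**Exclusion.** Protocol 9.3 removes a participant from the PPAS under this condition: "Participant received a Category 2 or Category 3 therapy / medication / as stated in Section 6.5". SAP 5.2.3 carries it over: "Participant received a Category 2 or Category 3 therapy /medication / as stated in Section 6.5 of the Protocol". Neither gives a time limit. The SAP adds that the conditions "may be detailed and completed if necessary following the data review", with any change settled before database lock and recorded in an SAP update.

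**Use.** PPAS-IAS and PPAS-CMI are subsets of the PPAS. Under SAP 5.2.5, PPAS-IAS is the main set for primary, secondary and non-CMI exploratory immunogenicity, and PPAS-CMI for the CMI analyses, each confirmed on the FAS. Efficacy uses both FAS and PPAS-IAS.

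**The concern.** A per-protocol set is meant to remove departures from the protocol. Here, taken together, the rules remove people for something the protocol says they may do. The exclusion applies to the whole participant, so it can also discard samples drawn before the influenza vaccine was given and which it cannot have affected.

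Influenza vaccine is the product most exposed to this. Most Category 2 products stop being recorded once the follow-up after an injection ends, whereas influenza vaccine is collected to the end of the study. COVID-19 vaccine is also collected late, but SAP 5.1 gives it its own rule: data before receipt are analysed and later data are listed. Influenza vaccine has no such rule.

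Two things are at stake: the size of the main immunogenicity set, and, for an analysis cut at D36 or D43, whether the set is thinned equally in the two cohorts. Protocol 4.2 treats the D22 and D36 titers as the basis for choosing the injection schedule.

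**Working it through.** **Step 1. The rules applied to one participant.** Suppose a Cohort 2 participant receives influenza vaccine on D150. That is 149 days after D01 and 128 days after D22, so it is within the allowance. It is a vaccine other than the study vaccine, so it fits the Category 2 example. SAP 5.2.3 then removes the participant, including the D22 and D36 samples drawn 128 and 114 days earlier. SAP 5.2.3.1 does not rescue them: it works sample by sample only for samples outside the time window or without a valid result.

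**Step 2. The plan's own figures.** From Protocol Table 4.2, the adjuvanted vaccine arms give:

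- Cohort 1 (Groups 1-4): 4 × (20 + 10) = 120.
- Cohort 2 (Groups 6-9): (20 + 60 + 20 + 60) + (10 + 30 + 10 + 30) = 240.

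These match the 120 and 240 in Protocol 9.2 for the injection-schedule contrast. The documents give no figure for expected PPAS losses.

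**Step 3. Days on which influenza vaccine is permitted.** A day after D01 is permitted if it is at least 14 days after every earlier study injection and at least 14 days before every later one.

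- Cohort 1: from 1 + 14 = D15. Before a D36 draw: D15-D35, 21 days.
- Cohort 2, between injections: on or after D15 and on or before 22 - 14 = D08, which is impossible. After the second injection: from 22 + 14 = D36. Before a D36 draw: 0 days.
- Visit windows: a Cohort 1 draw as late as D43 gives D15-D42, 28 days. In Cohort 2, a second injection on D29 and a draw 21 days later (D50) give D15 and D43-D49, 8 days.

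| Exclusions counted up to | Cohort 1 | Cohort 2 |
|---|---|---|
| Before the D36 draw, nominal | 21 | 0 |
| Before the D36 draw, with visit windows | 21-28 | 0-8 |
| D43 cut | 29 | 8 |
| D181 / D202 | 167 | 167 |
| D366 / D387 | 352 | 352 |

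**Step 4. Size, on assumed uptake.** Influenza vaccine uptake is not in the documents. Let *u* be the share of Cohort 1 vaccinated during D15-D35, assumed to be 5% to 30%. The loss is 120 × *u*. With an unchanged standard deviation, the confidence interval on the log titer widens by a factor of 1/√(1 - *u*).

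| *u* | Lost of 120 | Left | Width factor |
|---|---|---|---|
| 5% | 6 | 114 | 1.026 |
| 10% | 12 | 108 | 1.054 |
| 20% | 24 | 96 | 1.118 |
| 30% | 36 | 84 | 1.195 |

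On the nominal schedule, Cohort 2 loses 0 of 240 by this route before D36.

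**The case against.** The case for leaving the text alone has real weight.

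- **Category 2 needs judgment.** It is defined by possible effect on the immune response and illustrated by examples. The sponsor could decide at data review that a spaced influenza vaccine does not belong, and SAP 5.2.3 provides for that before lock. This stands as a route to a cure, but the current text does not take it.
- **The FAS keeps everyone.** SAP 5.2.5 confirms the immunogenicity results on it. That is a genuine check, but PPAS-IAS still supplies the main result.
- **Permitted conduct may still be excluded.** Removing a possible immunological confounder from a per-protocol set is defensible, and the plan does so for data after a COVID-19 vaccine. That supports dropping samples taken after influenza vaccine; it does not support dropping samples taken before it.
- **The main decision may be past.** SAP 5.4 confines dose selection to the first interim and records a partial lock. SAP 5.7 says the formulation is no longer being investigated further. This limits what a change can now affect. It also means that a change would come after the sponsor's group-level unblinding.

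A reader might infer that the cohort imbalance runs through the whole trial, or that only Cohort 1 can ever lose participants before D36. Step 3 supports neither: the permitted windows are equal over full follow-up, and visit windows open up to 8 days in Cohort 2. Influenza vaccine given at least 2 weeks before D01 may also be recorded, and would affect both cohorts alike.

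**Conclusion.** The inconsistency is real: followed as written, the rules remove compliant participants and discard valid earlier samples. Its effect depends on when exclusions are counted, and the two effects should not be added together.

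- **Counted to the D36 draw or the D43 cut:** losses fall almost entirely on Cohort 1 and touch the 120 versus 240 contrast. At 5-30% uptake over D15-D35, 6 to 36 of 120 are lost and the Cohort 1 interval is about 3-20% wider.
- **Counted over the whole study:** the permitted windows are equal, and the harm is avoidable loss of data in both cohorts.

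The loss figures rest wholly on assumed uptake. A reader might go further and conclude that the schedule comparison was biased, or that a large share of all 440 participants would be excluded. The documents support neither conclusion. They give no uptake, do not say how the first interim treated such participants, and offer nothing to show that recipients respond differently. The study is descriptive, and the FAS analysis would expose a material discrepancy. This is a defect worth correcting in the definition of the main analysis set; it does not show that results are wrong.

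**What to change.** In SAP 5.2.3, before any remaining database lock, state three things:

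1. Influenza vaccine received within the E03/TCI02 allowance is recorded but is not a Category 2 reason for exclusion from the PPAS.
2. It never removes samples drawn before it.
3. Only influenza vaccine outside the allowance excludes.

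As a sensitivity analysis, repeat the D36 and persistence (D181/D202 and D366/D387) GMTs without samples taken after influenza vaccination. Report how the first interim lock handled these participants and how many there were in each cohort.

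The cost is a short SAP addition and one extra set of tables from data already collected. There are two downsides. The per-protocol set will keep some people with a spaced influenza vaccine, which the sensitivity analysis addresses. And for data already unblinded at group level, the change must be documented as made after the first interim. No clinical rule changes.
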